## **10.3.** Pharmacodynamic/Hemodynamic Assessments

#### 10.3.1. Right Heart Catheterization Hemodynamic Assessments

During the RHC assessments, an experienced cardiologist or designee will measure the following hemodynamic parameters: CO/CI, PCWP, right atrial pressure (RAP), systolic/diastolic pulmonary arterial pressure (PAS/PAD), systemic vascular resistance/systemic vascular resistance index (SVR/SVRI), pulmonary vascular resistance (PVR), and pulmonary artery pulsatility index (PAPi). Additional hemodynamic parameters may be assessed, if deemed necessary.

RHC measurements of hemodynamic eligibility criteria will be performed at Baseline on Day 1 to determine subject eligibility, no less than 1 hour following RHC insertion. PCWP will be assessed by 2 successive measurements at least 10 minutes apart. CI measurements will be based on the average of 3 individual thermodilution recordings, with no delay between recordings. PCWP and CI measurements are required to be within 10% and 15%, respectively, of each other (Note: The lower value must be within 10% or 15% of the higher value, respectively).

Baseline hemodynamic parameters measurements will be performed after at least 2 hours following RHC insertion and stabilization (and preferably within 1 hour of assessment of hemodynamic eligibility criteria), and immediately before the start of study treatment administration. The Baseline CI measurement will be based on the average of 3 individual thermodilution recordings, with no delay between recordings. Additional recordings may be taken as needed until the final 3 recordings are within 15% of each other (Note: The lower value must be within 15% of the higher value). During Dosing and Postdose Periods, CI measurements will also be based on triplicate thermodilution recordings performed the same way as the Baseline CI measurement.

Additional details regarding the procedures for collection, transfer, and analysis of RHC data will be provided in a separate operation manual by the RHC core lab. Planned timepoints for RHC assessments are provided in the Schedule of Assessments (Table 4).

#### 10.3.2. Vital Signs (Blood Pressure and Heart Rate) Assessments

The following vital sign parameters will be measured as a component of the following PD assessments: SBP, diastolic blood pressure (DBP), mean arterial pressure (MAP), and HR.

Vital signs (SBP, DBP, HR) will be measured and MAP will be calculated. The same equipment should be used whenever possible through the study; however, during the RHC assessment period, the same equipment must be used. During RHC assessments, vital signs should be collected within  $\pm$  5 minutes of hemodynamic parameter measurements. For subjects with atrial fibrillation, HR should be assessed by pulse measurement over at least 30 seconds.

Planned timepoints for SBP, DBP, and HR assessments are provided in the Schedule of Assessments (Table 4).

## **10.3.3.** Echocardiography Assessments

During the ECHO assessments, an experienced sonographer will measure cardiac structure and function, including the following hemodynamic and cardiac function parameters: Stroke volume (SV), SV index (SVI), LVEF, fractional shortening (FS), left ventricular global longitudinal strain (LVGLS), left ventricular circumferential strain (LVGCS), left ventricular end-systolic/left ventricular/end-diastolic volume (LVESV/LVEDV), E, A, E', S', early/late diastolic velocities (E/A) ratio, early mitral filling velocity/early diastolic mitral annular velocity (E/E') ratio, tricuspid annular plane systolic excursion (TAPSE), tricuspid regurgitation (TR) velocity, and left atrial (LA) volume index.

LVEF at Screening will be assessed by ECHO to determine subject eligibility; however, historical LVEF can be assessed by other modalities (eg, cardiac magnetic resonance imaging (CMR), computed tomography (CT), nuclear imaging, catheterization).

Additional details regarding the procedures for collection, transfer, and analysis of ECHO data will be provided in a separate operation manual by the ECHO core lab. Planned timepoints for ECHO assessments are provided in the Schedule of Assessments (Table 4).

## 10.3.4. Markers of Renal Function, Urine Output, and Body Weight

The following markers of renal function will be measured: eGFR (calculated using the CKD-Epi equation), BUN, cystatin C, urine protein/creatinine ratio, and urinary sodium excretion (Table 2). These assessments will be based on blood and spot urine sampling.

Blood samples for eGFR to determine subject eligibility will be assessed centrally during the Screening Period; however, if it is not possible to obtain central laboratory results for Screening assessments prior to Day 1, local laboratory assessments may be used instead for determining eligibility (Section 10.2.8). At all other timepoints eGFR analysis will be performed by the central laboratory. Detailed instructions regarding blood and urine sample collection, processing, shipping, and analysis for markers of renal function will be provided in a separate laboratory manual. The planned timepoints for blood/urine collection are provided in the Schedule of Assessments (Table 4).

Urine output will be assessed during prespecified intervals by having the subject empty his/her bladder and capturing the urine volume at timepoints indicated in the Schedule of Assessments (Table 4), beginning with Baseline (subjects will be asked to void prior to RHC insertion) followed by 2-hour intervals during the IV infusion (Dosing Period). During the Postdose Period, urine output will be measured during the following intervals in relation to the start of the IV infusion: 6 to 10 hours and 10 to 24 hours. Any urine collected during the spot urine sampling should be accounted for in the total volume of the appropriate interval. During these intervals, the urine samples will be pooled for assessment of both urine volume and PK assessments (Section 10.4).

Body weight will be evaluated as indicated in the Schedule of Assessments (Table 4).

#### 10.3.5. Cardiac Biomarkers

The following cardiac biomarkers will be measured: NT-pro-BNP and hs-cTnT (Table 2).

Blood samples for cardiac troponin (hs-cTnT, hs-cTnI, cTnT, or cTnI) to determine subject eligibility will be assessed locally during the Predose Period, and in certain circumstances during the Screening Period (Section 10.2.8). At all other timepoints hs-cTnT analysis will be performed by the central laboratory. Detailed instructions regarding blood sample collection, processing, shipping, and analysis for cardiac biomarkers will be provided in a separate laboratory manual. Planned timepoints for blood collection are provided in the Schedule of Assessments (Table 4).

## **10.4. Pharmacokinetic Assessments**

Blood samples for plasma PK analysis of APD418 will be collected at the following timepoints in relation to the start of the IV infusion: At Baseline (within 2 hours prior to the start of study treatment administration), during the Dosing Period at 0.5, 1, 2, 3, 4, 5, and 6 hours (within 10 minutes before the end of the IV infusion), and during the Postdose Period at 6.083, 6.167, 6.25, 6.5, 7, 8, 10, 18, and 24 hours, as indicated by PK blood sample footnote in the Schedule of Assessments (Table 4). Detailed instructions regarding sample collection, processing, and shipping will be provided in a separate laboratory manual.

Pooled urine samples for PK analysis of APD418 will be collected during the following intervals in relation to the start of the IV infusion: Baseline (within 2 hours prior to the start of study treatment administration), during Dosing Period (0 to 6 hours), and during Postdose Period at the same intervals as for urine output (6 to 10 hours and 10 to 24 hours), as indicated in Section 10.3.4 and the Schedule of Assessments (Table 4). Any extra urine collected during the spot urine sampling (Section 10.3.4) should be included in the above pools. Detailed instructions regarding sample collection, processing, and shipping will be provided in a separate laboratory manual.

Drug concentration information that may unblind the study will not be reported to investigative sites or blinded personnel.

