## 6.3. Dosage and Administration

Each subject will receive a single dose as an IV infusion (APD418 or placebo) over a duration of 6 hours. The initial APD418 dose to be studied in Cohort 1 of Part A will be 0.17 mg/kg/h (1 mg/kg). Planned doses for the remaining 4 cohorts in Part A are 0.50, 1.0, 1.5, and 2.0 mg/kg/h or 3, 6, 9, and 12 mg/kg, respectively. Doses for each subsequent cohort may be adjusted depending on the safety, tolerability, and PK results of previous cohort(s). The maximum dose in the study will not exceed 2 mg/kg/h (12 mg/kg) without a protocol amendment. At the conclusion of Part A, 2 APD418 doses will be selected for expansion in Part B based on unblinded safety/tolerability and PD data. Additional details about the dose escalation and the dose selection process are described in Sections 10.6.2 and 11.9. Separate cohorts of subjects will be used for each dose level.

The study treatment will arrive at the site blinded and will be administered in a blinded fashion to the subjects. A delegated pharmacist or designee will be responsible for providing APD418 or placebo to the delegated qualified study personnel for administration as per the randomization scheme. Dilution instructions will be provided in a separate pharmacy manual. Placebo and APD418 treatments will be diluted based on the body mass of the subject and the assigned cohort dose level. Study treatment will be administered intravenously. Larger peripheral veins (ie, in the upper forearm) are advised for IV administration and (see Section 4.2). the infusion site will be noted as well as a change in the infusion site, if applicable. Selection of vascular access shall include assessment of the patient's condition of the vasculature at the insertion site and proximal to the intended insertion site, including condition of skin at intended insertion should be avoided as well as veins that are compromised (ie, sclerosed, corded, infiltrated). Additionally, it is advised to avoid extremities with impaired circulation, such as that caused by lymphedema. Hour 0 will correspond to the start of the IV infusion. The exact clock time of the start and end of the IV infusion will be recorded.

The location of IV infusion will be examined prior to start of infusion as well as anytime when a subject reports any relevant signs and symptoms such as swelling, redness, pain, tingling and/or burning sensation etc, which should be reported as AEs when appropriate.

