## 6.3.1. Dose Interruptions

Dose interruptions should be avoided if possible. The IV infusion can be interrupted upon any sign of clinical concern or if a subject complains of pain, burning or stinging sensation at or around the insertion site or anywhere along the venous pathway. Prompt recognition and timely, appropriate action should be instituted to prevent any complication(s) and/or prolonging subject discomfort. If a mechanical issue (eg, occlusion or infiltration of IV lines) is identified or if the peripheral line is not well tolerated, the IV infusion site may be changed to another infusion site or a central line. The IV infusion may be interrupted to address these issues for up to 30 minutes. Following the interruption, the IV infusion should be resumed to complete the planned full

6 hours. However, in the event of an infusion site related AE, the subject may be discontinued from treatment at the discretion of the Investigator, as described in Section 10.6.1.

Subjects experiencing any type of infusion site AE should be closely observed for at least 24 hours after dosing or until symptom resolution, and should be clinically handled in accordance with the standard medical practice and relevant guidelines. At the conclusion of the Postdose in-clinic observation period, subjects who do not achieve complete symptom resolution but are improving and are stable for discharge should be instructed to monitor the affected area.

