# 6.7. Treatment Compliance

Treatment compliance will be assessed based on the administration of a single IV infusion (APD418 or placebo). The IV infusion will be performed by a delegated qualified personnel. Prior to and following IV infusion, the qualified designee will visually inspect the infusion site and the infusion bag to ensure that the subject has received the entire dose.

The date, time, and duration of the IV infusion will be documented. Comments will be recorded if there are any deviations from the planned IV infusion procedures. In the case of an incomplete dosing (ie, caused by an interruption of IV infusion for longer than 30 minutes) as assessed by the dose administration staff, the Investigator, and/or the Sponsor, the subject will be discontinued from study treatment (Section 8.1).

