a Screening period for Part A is up to 21 days prior to (and including) Day 1. Screening period for Part B is up to 14 days prior to (and including) Day 1.

b Predose assessments are performed on Day 1 prior to RHC insertion (Hours > -2), including certain assessments for confirmation of eligibility.

c Baseline assessments are performed over at least 2 hours from RHC insertion to start of study treatment administration (Hours –2 to 0), including confirmation of hemodynamic eligibility criteria and randomization, followed by all other assessments ending with Baseline hemodynamic parameters measurements.

d Dosing Period to occur over 6 hours from start to end of IV infusion (Hours 0 to 6).

e Postdose Period to occur over 18 to 24 hours from end of IV infusion (Hours 6 to 24 [+ 6 hours]).

f Subjects are discharged at the Investigator's discretion based upon clinical presentation (if the patient's clinical state allows) and after all scheduled assessments at Hour 24 (+ 6 hours) have been completed.

g Follow-Up phone contact to occur on Day 9 (± 2 days) to assess for AEs and any changes to concomitant medications. Site staff will work with Early Termination subjects to obtain as much follow-up data as possible.

h Assessments can occur within 60 minutes of Hour 6, with priority on the RHC assessments occurring as close as possible to 6 hours after start of IV infusion/EOI. The following order of assessments should be followed, if possible: 12-lead ECG, ECHO, vital signs, RHC hemodynamic parameter measurements, blood sampling, EOI, urine sampling.

-  Subjects who discontinue study treatment prior to the end of the full 6-hour IV infusion will immediately, if possible, complete the EEOI assessments followed by all Postdose Period/Follow-Up assessments. In such situations, order of assessments specified in footnote "h" can be modified, but the priority should be given to RHC hemodynamic parameter measurements, vital signs, and blood sampling occurring as close as possible to EOI.
- j Only weight. The weight collected during the Predose Period will be used to calculate the subject's dose.

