- s Urine output is assessed during prespecified intervals by having the subject empty his/her bladder and capturing the urine volume at indicated timepoints. Any spot urine samples collected during the intervals will be accounted for in the total volume for that specific interval. Urine output is assessed during the following intervals in relation to the start of the IV infusion: Baseline (within 2 hours prior to study treatment administration), every 2 hours during the IV infusion (at Hours 2, 4, and 6), and during the Postdose Period at 6 to 10 hours and 10 to 24 hours intervals.
- t Local laboratory assessments may be used for determining eligibility at Screening under certain circumstances; refer to Sections 10.2.8, and 10.2.9 for clinical laboratory assessments (and serum pregnancy) and urinalysis, respectively.
- u Serum pregnancy test is performed for female subjects of childbearing potential to determine eligibility at Screening. Urine pregnancy test is performed and a negative result is required to be documented for female subjects of childbearing potential at Day 1 prior to randomization to confirm eligibility. In case of positive urine pregnancy test, serum pregnancy test should be performed before the subject can be enrolled in the study.
- v It is not required to result the urine drug screen prior to randomization. If a urine drug screen cannot be obtained prior to study treatment administration due to the timing of events as required by subject safety considerations, then it can be obtained after study treatment administration and prior to discharge.
- w Continuous 6-hour IV infusion.
- x Blood samples for plasma PK are collected as denoted in the table above. In addition to the timepoints denoted in the table above, blood samples for plasma PK are collected during the Postdose Period at 6.083, 6.167, 6.25 hours. The collection at Hour 6 should be done within 10 minutes before EOI.
- y Urine samples for PK analysis are collected during the following intervals in relation to the start of the IV infusion: Baseline (within 2 hours prior to study treatment administration), 0 to 6 hours, 6 to 10 hours, and 10 to 24 hours.

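### Post-infusion PK samples are timed from the start of infusion, so a permitted pause of more than 5 minutes can put up to three of them inside the infusion

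*Combined protocol and SAP*

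**What the plan says.** **PK clock.** Section 10.4, repeated in the Synopsis, states: "Blood samples for plasma PK analysis of APD418 will be collected at the following timepoints in relation to the start of the IV infusion". The post-infusion samples are then listed "during the Postdose Period at 6.083, 6.167, 6.25, 6.5, 7, 8, 10, 18, and 24 hours". Section 6.3 fixes the origin: "Hour 0 will correspond to the start of the IV infusion". The column heading of Table 4 also counts from initiation of treatment.

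**Interruption rule.** Section 6.3.1: "The IV infusion may be interrupted to address these issues for up to 30 minutes". It continues: "Following the interruption, the IV infusion should be resumed to complete the planned full" 6 hours. Section 6.7 treats a longer stop as incomplete dosing ("caused by an interruption of IV infusion for longer than 30 minutes"), which leads to discontinuation of study treatment.

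**A second clock.** Some parts of the schedule count from the end of infusion instead. Table 4 footnote x says of the PK sample: "The collection at Hour 6 should be done within 10 minutes before EOI". Footnote e says: "Postdose Period to occur over 18 to 24 hours from end of IV infusion", yet equates that period with Hours 6 to 24. Footnote p places the two postdose right heart catheterization (RHC) readings at 0.5 and 1 hour within that period.

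**What depends on the samples.** Section 11.6.3 lists the distribution half-life as a PK endpoint. Section 1.4 reports that concentrations fell rapidly after infusion in Phase 1. Appendix A of the PK Note to File Addendum lists plasma concentrations summarized by treatment and timepoint (Table 14.2.6.1.1).

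**The concern.** The samples at 6.083, 6.167, 6.25 and 6.5 h are evidently meant as 5, 10, 15 and 30 minutes after EOI. They are that only if the infusion ends exactly at Hour 6. The protocol allows it to end later and says nothing about moving these samples. A site that follows the text would draw some of them while drug is still running.

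Two results are at stake. The dense early samples describe the initial fall, and they become uninformative about it if taken before the fall begins. Summaries by nominal time would also average concentrations at or near the plateau with concentrations already declining. A Part A cohort has only 5 subjects planned on active drug, so one such subject has visible weight. Section 6.3 has the exact start and end of the infusion recorded, so the problem can be detected afterwards, but a sample that was not drawn after EOI cannot be recovered.

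**Working it through.** **Inputs.** Planned infusion 6 h (Section 6.3); permitted pause d from 0 to 30 minutes (Section 6.3.1); nominal PK times from the start (Section 10.4); Hour 6 PK sample within 10 minutes before EOI (Table 4, footnote x). Assumption: completing the full 6 hours means 6 hours of infusing time at an unchanged rate.

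**Formulas.** EOI = 6 h + d/60. Minutes from EOI to a sample at nominal time t = 60 × (t − 6) − d. A negative value means that drug is still infusing.

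**Check with no pause (d = 0).** The samples at 6.083, 6.167, 6.25, 6.5 and 7 h fall 5, 10, 15, 30 and 60 minutes after EOI. The schedule is coherent in this case.

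**With a pause** (minutes relative to EOI):

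| Pause d (min) | EOI (h) | Hour 6 sample due (h) | 6.083 h | 6.167 h | 6.25 h | 6.5 h | 7 h |
|---|---|---|---|---|---|---|---|
| 0 | 6.000 | 5.833–6.000 | +5 | +10 | +15 | +30 | +60 |
| 5 | 6.083 | 5.917–6.083 | 0 | +5 | +10 | +25 | +55 |
| 10 | 6.167 | 6.000–6.167 | −5 | 0 | +5 | +20 | +50 |
| 15 | 6.250 | 6.083–6.250 | −10 | −5 | 0 | +15 | +45 |
| 20 | 6.333 | 6.167–6.333 | −15 | −10 | −5 | +10 | +40 |
| 30 | 6.500 | 6.333–6.500 | −25 | −20 | −15 | 0 | +30 |

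The 6.083, 6.167 and 6.25 h samples are on-infusion when d exceeds 5, 10 and 15 minutes respectively. The 6.5 h sample is never strictly on-infusion. At d = 30 the Hour 6 window opens at 6.333 h, after the third nominally later sample (6.25 h), so the order is inverted. The first sample clearly after EOI is then the one at 7 h.

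**Effect on a cohort mean (illustration on assumed values).** Suppose one of 5 subjects pauses from 3.0 to 3.5 h. Let f be the share of the end-of-infusion concentration in the distribution phase, h the distribution half-life in minutes, and 3.5 h the terminal half-life. An uninterrupted subject at 6.5 h is then at u = f × 2^(−30/h) + (1 − f) × 2^(−0.5/3.5) of peak, where 2^(−0.5/3.5) = 0.906. The paused subject, at EOI, is at about 0.98 of that peak. The inflation of the 6.5 h mean is (1/5) × (0.98/u − 1).

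- f = 0.3, h = 30: u = 0.150 + 0.634 = 0.784; inflation = 0.2 × 0.25 = 5%.
- f = 0.7, h = 10: u = 0.0875 + 0.272 = 0.359; inflation = 0.2 × 1.73 = 35%.

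The documents give none of f, h or the terminal half-life. The range shows only that the size is driven by assumption, at the longest permitted pause.

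**After re-anchoring.** At d = 30, samples at EOI + 5, 10, 15, 30 and 60 minutes fall at 6.583, 6.667, 6.75, 7.0 and 7.5 h from the start. All are post-infusion and all follow the Hour 6 sample.

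**The case against.** The strongest reply is that this is a wording gap in three PK samples. Interruptions are to be avoided where possible, infusion start and end times are recorded, and detailed collection instructions sit in a laboratory manual that is not among the documents and may supply the right anchor. The pre-EOI sample still captures the end-of-infusion level, and the PK limits on escalation in Section 10.6.2 use Cmax and AUC0-∞, not the distribution half-life. If the full 6 hours meant clock time, EOI would stay at Hour 6 and the problem would vanish. All of this stands as a limit on severity. None of it supplies a re-anchoring rule in the protocol, and infusing time is the more natural reading of resuming to complete the infusion.

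A reader might also infer more than the documents support:

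- **Postdose RHC is mistimed.** Not so. Sections 3.1 and 9.2 count it from cessation of treatment, footnotes e and p from the Postdose Period, and Section 11.6.4 from the end of infusion. Only the general column heading of Table 4 differs.
- **All four early samples fall on-infusion, or every interrupted subject loses them.** The 6.5 h sample at worst coincides with EOI, and a pause of 5 minutes or less puts no sample on-infusion.
- **Early-stopped subjects have no sample near EOI.** Section 9.4.1 and footnote i call for immediate early-end-of-infusion assessments where possible, with priority for blood sampling. What is missing is a clock for the later samples.
- **About 12% of infusions will be interrupted.** The 12% in Section 1.4 is the Phase 1 rate of infusion-site adverse events at comparable doses, not of pauses.
- **AUC0-6 is biased by the sampling times.** Its fall, about 9% in the assumed model, comes from the pause itself and would be the same under any post-infusion clock.

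**Conclusion.** The point holds for PK sampling and is minor. Followed as written, a pause of more than 5 minutes puts at least one nominally postdose sample on-infusion, and a pause of more than 15 minutes puts three there. At 30 minutes the fourth sits at EOI and the Hour 6 sample comes after the first three. In such subjects the early decline is poorly sampled or missed, and means by nominal time mix on- and off-infusion values.

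This rests on reading the full 6 hours as infusing time and on the laboratory manual not providing another anchor. The number of subjects affected cannot be estimated, because no interruption rate is given. The effect on a mean depends on half-lives that the documents do not state. The primary endpoint does not use these samples and is not affected.

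**What to change.** In the Synopsis, Section 10.4 and Table 4 footnote x, state the post-infusion PK times from actual EOI: EOI + 5, 10, 15 and 30 minutes, then 1, 2, 4, 12 and 18 h. These are the present nominal times minus 6 h. State that the same clock applies after an early end of infusion, where footnote i requires prompt blood sampling but gives no times for what follows. Align the Table 4 column heading with footnotes e and p, which already count postdose RHC from the end of infusion, so that PK and RHC share one clock. Section 6.3.1 should say expressly whether the 6 hours are infusing time or clock time.

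The cost is wording in the protocol and any matching text in the laboratory manual. No samples are added and nothing changes for an uninterrupted subject. In interrupted subjects, post-infusion samples move by up to 30 minutes; at 18 and 24 h that lies within the windows of +3 h and +6 h that Table 4 already allows.
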